- 2. Ask about claustrophobia.
- 3. Schedule an appointment in the Calpendo for 30 minutes (the actual scan takes 30-40 minutes + time for removing metal, wanding and paperwork, etc.)
 - a. Schedule scans at least 24 hours in advance.
 - b. NYU staff will communicate subject availability and relevant forms to NYSPI coordinator within 5 days of successful screen being confirmed.
 - c. Request the patient to be at least 30 minutes early. If NYU subject, both RC and subject will arrive 30 minutes in advance of scan.
 - d. Scan cancellation needs to be 95 hours (4 days) before scheduled scan. NYU staff will communicate cancelations to NYSPI staff so that the official cancelation can be made in Calpendo.

ON THE DAY OF THE SCAN for Research Coordinator:

- 1. Bring the subject in to the MRI suite along with caregiver if needed. The caregiver can wait in the waiting area.
- 2. NYSPI RC will give the consent form and metal questionnaire (and clearance if needed) to the tech first.
- 3. NYSPI RC will get billing form from [name], check box to indicate we want a neuro read. Fill out the rest of the form and return to [name].
- 4. Make sure subjects remove all metals pins, clips, credit cards etc.
- 5. NYSPI RC will wand the patient to make sure there are no other metals.
- 6. The tech will check and then take the subject into the scanner room.
- 7. RC must go in to help place the subject in a comfortable position.
- 8. RC should wait with the technician outside the scanning room and keep an eye on the patient throughout the duration of the scan. If the RC notices excessive movement, they should notify the tech about the possibility of re-running that scan section.
- 9. The tech can instruct the subject over the intercom.

AFTER THE SCAN:

- The RC should enter the scan room and make sure that the subject gets out of the scanner carefully.
- Let them collect their belongings and take them out of the MRI suite.
- The study will be uploaded to XNAT (NYSPI).
- Go to XNAT.nyspi.org and check in your projects and download when ready (NYSPI RC).
- You can then download the scan to a PC or MAC and then send it over NYSPI file transfer or burn on CDs and send them to the respective sites.
- RC will print the MRI report for PI or study physician to review and sign it. PI or study physician will sign and date at bottom of page. Make sure this is completed in clear handwriting.

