Hypothesis 3. Patients treated with valacyclovir will show less accumulation than patients on placebo in PET amyloid scans' (18F-Florbetapir, 0 to 78 weeks) combining six ROIs (SUVR: cerebellar reference) that show increased uptake in AD: medial orbital frontal, anterior cingulate, parietal, temporal, posterior cingulate, precuneus.

Hypothesis 4. From baseline to 78 weeks, patients treated with valacyclovir will show smaller increase in 18F-MK-6240 binding (SUVR: combining medial temporal, lateral temporal, prefrontal, parietal, and occipital regions of interest, ROIs, with cerebellar reference) than patients treated with placebo.

18F-MK-6240 PET imaging was funded by a grant supplement within the first year after study initiation and conducted in a subset of the overall sample.

In exploratory analyses, we will compare valacyclovir to placebo for changes in global cognition (MoCA), verbal memory (Craft story delayed verbatim recall), and examine age, sex and apolipoprotein E e4 genotype as a potential moderator of outcome. We will explore the AD "signature" of regional cortical thinning and whole brain cortical thinning on MRI for

valacyclovir compared to placebo. We will evaluate plasma acyclovir levels. In the subsample with CSF acyclovir levels, we will examine CSF acyclovir levels and if a sufficient number of participants has LPs done for CSF, plasma/CSF acyclovir correlations will be examined.

Inclusion Criteria:

- 1. Females must be postmenopausal defined as 12 consecutive months without menstruation.
- 2. Diagnosis of probable AD by NIA clinical diagnostic criteria.
- 3. Folstein Mini Mental State (MMSE) score 18 to 28 (inclusive) out of 30.
- 4. Clinical Dementia Rating (CDR) score of 1 (mild dementia).
- 5. A family member or other individual who is in contact with the patient and consents to serve as informant during the study.
- 6. Patient retains capacity to consent for him/herself or retains the capacity to identify a surrogate who will consent on his/her behalf.

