The patient will then see the study physician, who will write a progress note and complete the MD NACC packet, the Concomitant Medications log, the CIBIC-Plus, and the CDR. The physician will also complete the ADCS-ADL with the informant. This informant interview can be done over the phone at a later time within the Baseline period, as well.

The coordinator will then draw blood for APOE genotyping (yellow top), which is to be stored at the Human Genetics Resources Core (HGRC). Both NYU and NYSPI subjects will have APOE drawn at NYSPI during Baseline, as will BAI subjects. BAI staff will store APOE on site for later send out to the HGRC. The RC will fill out the HGRC form as described in the blood draw policy section of this manual. The form and tubes will be checked by the RC who filled them out and the back-up RC. They will sign the corresponding accuracy log.

An extra serum tube (red top) will also be drawn for all subjects, processed, and stored in the -80 freezer on Pardes floor 4 (at NYSPI, BAI will store locally). Please see the Lab manual section for greater processing description.

As described in the consent forms, all clinically applicable information collected during the trial will be disclosed to patients and their caregivers, as well as interpretation of baseline MRI, 18F-Florbetapir amyloid PET radiological read, and results from CSF analysis.

After the baseline evaluation, the results of outcome measures specified in the hypotheses will not be disclosed. Apolipoprotein E genotyping results will not be disclosed nor will results from 18F-MK-6240 tau PET scan; tau PET imaging results are still in research development and there is no standardized method to make a clinical read and provide a report to the patient.

At both sites, the medication kit is dispensed when the study physician sees the patient and reviews the medication kit.

After all procedures for the day are completed, follow-up visits are scheduled. The RC must review the Checklist for the visit and ensure that all forms listed in it are completed on the checklist page before the patient leaves the clinic. The RC will double check that the study physician has completed all necessary forms, as well. After all verifications are complete, the patient and caregiver may be sent home.

A few important notes to keep in mind at Baseline:

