- ADAS-Cog11, NACC neuropsychological battery, NACC RC questionnaire forms, vital signs. (RC completes at NYSPI, delegated/certified staff at NYU and BAI).
- No blood will be drawn.
- Before the patient leaves, the research coordinator will double check that the study physician completed
 all necessary forms. After verification is complete, the coordinator will confirm that all RC forms have
 been completed, as well. The RC must check the Checklist for the visit and ensure that all forms listed in
 it are completed and ticked off on the checklist page. Only after both of these checks have taken place
 can the patient and caregiver be sent home.

Week 78 Visit or Endpoint (dropout) visit

End of Study Procedures: We will not break the blind at Week 78. We will only break the blind after the entire clinical trial is over and the final subject enrolled completed all week 78 procedures. We will provide all test and procedure results to the referring MD, then let the referring MD decide what to do in terms of prescribing valacyclovir. The RC will need to summarize cognitive testing over protocol duration, in preparation. A full report inclusive of the subject's experience in the study will be provided in addition to the cognitive testing summary (see below).

These measures will span over 2-4 clinic visits.

- This visit follows a very similar protocol to the week 0 visit, with the addition of blood drawn for SMAC, CBC, and HSV antibodies.
- The RC will fill out the Quest forms and tubes as described in the blood draw policy section. The form and tubes will be checked by the RC who filled them out, the back-up RC and the program manager. Those who check will be looking to make sure the patient initials, IRB number, correct collection time and date, language about research use only, and the 6447 and 90849 HSV Boxes are checked on the form. They will then compare these to the tube to make sure all is accurate and matching.
- NYSPI and NYU subjects will have MRI, PETs, and LP performed at NYSPI/CUMC as previously described in this manual and as described in each respective "Procedures" section. The NYSPI RC will fill out the LP and Plasma forms and tubes according to the LP procedure section of this manual. The form and tubes will be checked by the RC who filled them out, the back-up RC and the program manager.
- The RC will draw blood for plasma (lavender top), SMAC (red top), CBC (lavender top), and HSV (marble top) antibodies.

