[name], MD

[name], University of Pennsylvania Medical Center [name]

Notify UAB Antiviral pharmacology lab [contact], [contact]) when shipment leaves with FedEx air bill number. [contact] ([name] cell phone). Date and time. direct sig

Ship all samples with this form to:

[name]., Antiviral Laboratory Director

Lab Contact: [name], B.S.

University of Alabama at Birmingham Division of Clinical Pharmacology [name]

CSF Storage & shipment: HGRC

- 1. HGRC vials will not be stored on site, they will be dropped off at the HGRC on the day of the LP. The CSF for the HGRC will NOT be frozen, the specimens are dropped off at the HGRC same day of the LP, so freezing isn't necessary.
- 2. There should be four copies of each barcode number on separate stickers. A small sticker should be placed on each of the two cryovials, another (larger sticker) should be placed on the bio sample form, and the last (larger sticker) should be placed on the CSF biological storage log in the bio samples binder. Subject ID, PI, Collection date, and IRB protocol number will also be included in the cryovials brought to the HGRC.
- 3. The RC should fill out the CSF Bio Sample form from the HGRC with the information specified, including the matching barcode sticker.
- 4. The RC should make a copy of this form and bring it to the HGRC. HGRC will keep the copy and sign the original. The signed original should then be copied. One copy of the form should be kept in the patient's chart, and the other should be kept in the bio samples binder.

CSF Analysis and Reports: UAB and UPenn

- a. UPenn: On a quarterly basis, tau, ptau, and AB42 will be analyzed and reported for all subjects. Neurofilament Light (NL) will be analyzed and reported on as well. The site will receive report of NL results, but these results will not be shared with subjects. Only baseline CSF analyses of tau, ptau and AB42 will be shared with subjects.
- b. UAB: At Weeks 12 and 78, plasma acyclovir levels will be drawn and analyzed for all subjects. On a quarterly basis, week 12 and 78 plasma acyclovir levels will be reported to the site, but not shared with subjects. This test isn't clinically relevant but is of relevance to the research team as a check on randomization and subject drug compliance.

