18F-Florbetapir Amyloid PET Imaging Procedures (NYSPI/NYU specific, BAI will follow this protocol with modification made per facility standard) — Week 0 & Week 78

Scheduling:

- a. NYSPI Coordinator uses iLab to fill out the time request form. Each participant will need a separate request (if there are 3 participants, 3 separate requests will need to be initiated). NYU staff will communicate subject availability and relevant forms to NYSPI coordinator within 1 day of successful screen being confirmed.
- b. Confirm if the available dates work with the subject's schedule. If not, follow up with potential dates.
- c. Coordinator officially requests a slot. Please note slots are first-come-first-serve. It is best to try to schedule as far in advance as you can per protocol.
- d. Coordinators will need to attach all the necessary forms including a scanned copy of the signed consent form, the scan requisition form, and the pregnancy attestation form.
- e. NYSPI coordinator will also need to create an order in EPIC for the PET scan, in tandem with iLab. Both the order in EPIC and the request in iLab are required to make an appointment.
- f. Amyloid PET scans are offered the following times on Thursdays: 14:00, 14:15, 14:30, 15:00, 15:15, and 15:30.
- 1) RPOs: The scan requisition form can be downloaded directly in iLab or from the server. Note that there are separate forms for amyloid and tau scans.
 - a. The date needs to be filled out in 01-Jan-2018 format. The scan requisition section needs to be digitally signed with a PDF editor.

- b. Use military time when filling out the time request form. Military time will be calculated in 24 hours. 12.00 am would be 0000 hours 12 pm would be 1200 hours and 11 pm would be 23 hours.
- 2) Pregnancy: All female patients need to be sign documentation prior to scheduling their appointment. The patient will also need to indicate the year of their last menstrual period.
- a. You may want to contact [name] ([contact]) regarding this process, she can also answer questions regarding the cancellation policy.

PET PRE-SCAN PROCEDURES:

- 1. During study screening:
 - a. check for inability to cooperate/claustrophobia (sedation is not offered for this protocol), inability to lie on scanner bed for 20 minutes, inability to achieve venous access sufficient for tracer administration, and past radiation exposure.
 - b. Have the patient sign the pregnancy attestation form if applicable.

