- 10. Patient will be at the PET center for about 1.5 hours (scan acquisition time is 20 minutes and the uptake time is 50 minutes). The RC will go back to the scanner 5 minutes before the scan time is up to retrieve the patient and sign a copy of the PET checklist.
- 11. Once the scan is done the RC will take the patient and caregiver back to the clinic to complete any other necessary measures or to the most convenient location to exit and head to their train or car, if NYU subject, they may leave at this time.

POST SCAN PROCEDURES:

- 1. Instruct patient that he/she can continue normal activities after PET scan.
- 2. Patient is advised to drink several glasses of water and contact study physician if there is any persisting pain in his/her hand or arm (slight soreness and bruising is expected since a small tube was inserted into vein of arm).

Obtaining Amyloid Scan Reads

(completed through the PET Department's Safety Read System in RedCap):

Amyloid reads will be completed by [name], MD ([contact]) and/or [name], MD ([contact]) Amyloid read reports are available in RedCap 1-10 days following amyloid PET scan.

To access an Amyloid read:

- 1. Website: https://radiosftp.cpmc.columbia.edu /redcap/redcap v8.11.7/DataEntry/record status dashboard.php?pid=31&pagenum=2
- 1. Navigate to "Record Status Dashboard" (on the left-hand side of the home-page) and all VALAD subjects are on the list of study subjects receiving reads that will automatically populate when one navigates to the Record Status Dashboard.
- 2. Subjects are identified on this list by "NYSPI #7537" followed by respective Study ID.
- 3.RCs must download a PDF the report with "saved data," print, file in subject chart and obtain signature and date on the amyloid read by the patient's study MD.

4. SUVR: Once the analysis and decisions about how to interpret SUVR are confirmed by [name], we will decide how to communicate results to subjects and caregivers, with Drs. [name] and [name]. [name] would like to be informed of discrepant cases (between amyloid pos/neg status and SUVR AD Dx interpretation).

Study physicians will review the amyloid read and SUVR results with the patient and caregiver when they come in for their next visit. If the patient wants the results sooner the physician may call to discuss but inperson discussion is strongly preferred. Some reads may require immediate follow up.

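### The amyloid PET section has read and SUVR results reviewed with families without limiting this to the week-0 scan, against the protocol's own non-disclosure rule, and nothing puts the week-78 ratings before release of the week-78 result

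*Protocol*

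**What the plan says.** Hypothesis 3 in the protocol's Specific Aims concerns florbetapir SUVR over six regions from 0 to 78 weeks: "Patients treated with valacyclovir will show less accumulation than patients on placebo in PET amyloid scans". SAP section 3 defines the imaging outcomes as change from baseline to week 78.

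The protocol's Week 0 (Baseline) Visit section sets the disclosure rule: "After the baseline evaluation, the results of outcome measures specified in the hypotheses will not be disclosed". Just before it, the same section lists what patients and caregivers will be told, "as well as interpretation of baseline MRI, 18F-Florbetapir amyloid PET radiological read, and results from CSF analysis". SUVR is not on that list.

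The amyloid section is headed "18F-Florbetapir Amyloid PET Imaging Procedures (NYSPI/NYU specific, BAI will follow this protocol with modification made per facility standard) — Week 0 & Week 78". Its part on obtaining scan reads has the coordinator download and file the report and the study physician sign and date it. Then: "Study physicians will review the amyloid read and SUVR results with the patient and caregiver when they come in for their next visit". On turnaround it says: "Amyloid read reports are available in RedCap 1-10 days following amyloid PET scan".

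The CSF analysis section, item a, carries an explicit limit: "Only baseline CSF analyses of tau, ptau and AB42 will be shared with subjects".

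Of the week-78 assessments, the protocol says: "These measures will span over 2-4 clinic visits".

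**The concern.** One section forbids telling families the results of hypothesis outcomes after baseline. Another tells the physician to go over such a result with them and does not confine this to the baseline scan. At NYSPI the people who handle or hear the result are also those who produce the clinical ratings. The coordinator who files the read gives the ADAS-Cog11. The physician who signs it rates the ADCS-ADL, CDR and CIBIC-plus. The caregiver who is told it may be the informant for the ADCS-ADL, the Hypothesis 2 outcome.

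If valacyclovir does slow amyloid accumulation, what raters and informants know about the scan could differ between arms even with drug assignment blinded. Expectation based on the scan could then move an informant-based rating, so that part of a biomarker effect appears as a functional effect. If the drug has no effect on amyloid, the same knowledge would add noise rather than a systematic difference.

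**Working it through.** No sample size, power or error-rate figure enters this point, so the check is a comparison of sections plus one timing calculation.

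**1. Which scans does the instruction cover?** The sentence on reviewing results names no time point. The section heading names weeks 0 and 78. The day-of-scan steps in the same section mention week 78 when they discuss the order of procedures and the updated consent form. The Week 78 visit section has the final scans follow the baseline procedure. The filing, signing and review steps carry no week-0 limit. The CSF section shows that the authors wrote such a limit when they wanted one.

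**2. Which result conflicts with the rule?** The protocol treats the radiologist's positive/negative read and the SUVR as separate results.
- SUVR: its change is the Hypothesis 3 outcome and it is not on the list of disclosable items. The conflict is clear.
- Visual read: it is not the Hypothesis 3 outcome, and it is on the list. The list opens with the word baseline, and it is unclear whether that word governs the PET read as well as the MRI. The rule is ambiguous here.

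**3. Is there a next visit at week 78?** Week 78 is the last scheduled time point, but its measures take 2 to 4 clinic visits. For NYSPI and NYU participants, amyloid PET slots are on Thursdays and tau PET slots on Mondays and Fridays, and the two scans must be at least 24 hours apart. With amyloid PET first:
- Thursday to Friday = 1 day
- Thursday to the following Monday = 4 days

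Both fall within the 1 to 10 days given for the read. A read can therefore be back by the tau visit, though it need not be. The tau section tells the coordinator to use the uptake period to administer protocol measures if the patient is able, so testing on that later day is foreseen. The physician may also telephone results sooner on request. No turnaround is given for SUVR and no spacing for the week-78 visits, so it cannot be established whether SUVR would be known in time.

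**4. Is any order imposed?** None that settles the matter. The amyloid section remarks that PET is usually not the first procedure at week 78. The Week 0 notes put the ADCS-ADL at the end of its visit, which orders measures within a visit but not between a scan and a later rating visit. Nothing requires the week-78 ratings to be finished before the week-78 read or SUVR is seen.

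**5. Which measures are exposed?** The ADCS-ADL most directly, because it rests mainly on the informant's answers and the physician's judgement; then the CDR and CIBIC-plus. The ADAS-Cog11 is a performance test given by the coordinator at NYSPI and is probably less open to expectation. This allocation of raters is NYSPI's. NYU and BAI use the site investigator or delegated, certified staff.

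**The case against.** The strongest reply is that this is loose drafting with no consequence. Week 78 ends the schedule, so a review at the next visit most naturally describes the week-0 scan. The Week 0 section holds the specific disclosure rule, which can be read as limiting the logistics text. The result that returns in 1 to 10 days is the read, which is not the Hypothesis 3 outcome. The amyloid section leaves the manner of communicating SUVR to a later decision. PET is usually not first, and the disclosure rule speaks of patients and caregivers, not of what staff may see.

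Much of this stands. It narrows the clear conflict to SUVR and makes exposure before rating a possibility that depends on scheduling. It also means that keeping results from raters is a recommended safeguard, not something the protocol already requires. It does not remove the conflict. After leaving SUVR communication open, the amyloid section goes on to direct physicians to review SUVR with families, and nothing there excludes week 78.

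A reader might go further and infer that the protocol has week-78 ratings made in knowledge of the Hypothesis 3 outcome, or that the blind is broken. The documents support neither. No section prescribes that sequence, an amyloid result does not disclose the assigned arm, and the Week 78 section keeps the blind until the last participant has finished.

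**Conclusion.** The disclosure instruction in the amyloid section conflicts with the Week 0 disclosure rule for week-78 SUVR, is unclear for the week-78 visual read, and lacks the baseline limit that the CSF section has. As written, the plan allows week-78 ratings after the week-78 amyloid result is known, without calling for it.

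The size of any effect on the ADCS-ADL, CDR or CIBIC-plus cannot be derived. The documents do not say how far such knowledge shifts a rating, how amyloid results would differ by arm, or how often a rating would follow a result. A systematic difference between arms needs three things together: a drug effect on amyloid, a result known before the rating, and a rater or informant influenced by it. The change is worth making because it removes an internal contradiction and protects an informant-based outcome at almost no cost.

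**What to change.** Reconcile the Week 0 disclosure rule, the amyloid section's review sentence and its sentence on reporting to NYU participants, so that routine disclosure of the amyloid read and SUVR applies to the week-0 scan only. Add that a participant's week-78 ADAS-Cog11, ADCS-ADL, CDR and CIBIC-plus must be completed before that participant's week-78 read or SUVR is released to the raters, patient or caregiver. Leave the existing provision for reads that need immediate follow-up as it is.

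The cost is a short delay before staff see and file week-78 reads, and families do not routinely receive week-78 amyloid results. No outcome data are lost.

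If visits are already complete, as the SAP's past tense suggests, compare the dated physician signatures on the week-78 reads with the dates of the week-78 ratings, and report how many ratings came after the read had been seen.
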